#### C MRS voxel tissue composition

In vivo MRS does not have the spatial resolution or the sensitivity to eliminate partial volume effects of different tissue types. Using an automatic MRS voxel segmentation program developed in our laboratory incorporating routines from MATLAB (Version 7.0.4, MathWorks, Natick, MA, USA) and SPM5 (The Wellcome Department of Imaging Neuroscience, Institute of Neurology, University College London, London, England), the relative gray matter and white matter tissue components will be calculated and applied as correction to factors to the C enrichment curves.

#### **Plasma NMR spectroscopy**

The peripheral metabolism of infused C labeled substrates is a confounding factor when measuring metabolism in the brain. Acetate metabolism is known to occur in the liver, resulting in the synthesis of glucose by gluconeogenesis. In the brain, C labeled glucose produced in the liver would lead to isotopomer labeling patterns similar to the metabolism of [1, 2-C2] acetate resulting in a potential source of error in our experiments. As a result, the fractional C enrichment of all plasma glucose isotopomers will be calculated by C and H high resolution NMR using a Bruker 600 MHz spectrometer to correct brain isotopomer enrichment levels for the contribution of peripheral metabolism.

#### **DSC-Perfusion Weighted imaging**

A 2D single shot gradient echo echo-planar imaging (EPI) sequence will be used to obtain DSC\_PWI using the following parameters: TR/TE = 1700/40 ms, FA = 90°, slice thickness = 5mm, matrix size = 128, and 50 measures. Gadolinium-DPTA (Gd-DTPA) contrast (0.1 mmol/kg) will be administered intravenously at the completion of the 5th scan. The resultant images are transferred to an offline program where CBV, CBF and MTT maps will be generated for each slice. To calculate CMRO2, an arterial input function is chosen from the M1 section of the middle cerebral artery for each subject. A least squares exponential fitting is used to minimize secondary circulation; a singular value decomposition deconvolution is then used to obtain estimates of CBF and CBV.

To determine the effect of substrate limitation on glucose metabolism the position of the MRS voxel will be overlaid on CBF, CBV, and CMRO2 maps using an automatic image overlay program developed in our laboratory incorporating routines from MATLAB (Version 7.0.4, MathWorks, Natick, MA, USA). The relative CBF (ml/100g/min), CBV (ml/100g), and CMRO2 (ml/100g/min) within the region of the MRS voxel will then be compared to the final C Glu and Gln enrichment pools to determine if substrate limitation correlates with metabolite enrichment.

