### **Research Design and Methods**

#### Imaging Protocol Overview

All control and TBI subjects will undergo an identical MRS/MRI protocol and neurological exam. MRS/MRI will be performed on a 3T Siemens TIM Trio system equipped with a second radiofrequency channel (Siemens Medical Solutions, Erlangen, Germany) using a specially designed and manufactured  $^1\text{H}$ - $^{13}\text{C}$  dual tuned volume head coil (Advanced Imaging Research, Cleveland,

OH). Sagittal 3D T2 weighted (T2WI) and 3D T1 weighted (T1WI) MR images, reformatted in axial and coronal planes, will be obtained for image co-registration and segmentation. The 2D DSC-PWI sequence will be used to determine cerebral blood flow (CBF), cerebral blood volume (CBV), mean transit time (MTT), and the cerebral metabolic rate of oxygen (CMRO2). Detailed sequence description and image processing methods are explained below.

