#### ISIS-DEPT C MRS sequence

Using the T2WI images, a 7 x 5 x 6 cm^3 volume covering portions of the fronto-parietal lobe will be positioned, avoiding areas of obvious contusion. Direct detection, localized in vivo C MRS spectra will be acquired using a gradient-spoiled semi-adiabatic distortionless enhanced polarization transfer (DEPT) sequence (TR = 2.5 sec, interpulse delay = 3.8 ms, 45° flip angle, 128 acquisitions and WALTZ-16 decoupling applied during the acquisition) with three-dimensional image selected in vivo spectroscopy (ISIS) localization and outer volume saturation. Spectra will be post-processed off-line using NUTS data processing software (Acorn NMR Inc., Livermore, CA). All relevant peaks will be identified and assigned by comparison to previously published values, integrated, and the relative amount of C incorporation into Glu and Gln will be calculated. To calculate the various flux

parameters, a two-compartment model of flow from [1-C] glucose and [1, 2-C2] acetate will be implemented in CWave software using modifications of previously published equations.

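### A gray/white matter correction is specified for the 13C enrichment curves but not for the perfusion values from the same voxel that are compared with them

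*Combined protocol and SAP*

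**What the plan says.** The section on 13C MRS voxel tissue composition gives the reason for a correction: "In vivo MRS does not have the spatial resolution or the sensitivity to eliminate partial volume effects of different tissue types". It then says that "the relative gray matter and white matter tissue components will be calculated and applied as correction", and the only target it names is the 13C enrichment curves.

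The DSC-Perfusion Weighted imaging section uses the same voxel: "To determine the effect of substrate limitation on glucose metabolism the position of the MRS voxel will be overlaid on CBF, CBV" and CMRO2 maps. The values "within the region of the MRS voxel will then be compared to the final" 13C glutamate and glutamine enrichment pools, "to determine if substrate limitation correlates with metabolite enrichment". It states no tissue step and no summary measure (mean, median or other) for perfusion.

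The voxel is 7 x 5 x 6 cm. According to the ISIS-DEPT section, a volume covering parts of the fronto-parietal "lobe will be positioned, avoiding areas of obvious contusion". The Imaging Protocol Overview says that 3D T1 and T2 images "will be obtained for image co-registration and segmentation". The Statistical Analysis section plans Pearson coefficients, worded for metabolic or perfusion changes against neurological status, and names no covariate.

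**The concern.** A voxel of 7 x 5 x 6 = 210 mL in this region holds both gray and white matter. If the two tissues perfuse at different rates, voxel CBF varies between subjects with the tissue mix, even when perfusion within each tissue is the same. The protocol accepts this reasoning for the 13C signal and specifies a correction there. It does not carry the reasoning over to the other variable in the same comparison.

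This comparison is the only analysis described for the second objective, which asks whether perfusion limits the supply of substrate. Tissue-mix variation left in perfusion alone acts as noise and pulls the correlation towards zero. A weak correlation could then reflect weak coupling or uneven tissue content, and the data as summarised would not tell the two apart.

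**Working it through.** The documents give no expected correlation, variance or tissue fraction, so there is no planned figure to reproduce. The check has two parts: what the text specifies, and how large the effect could be on assumed inputs.

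**Text, side by side**

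| Step | 13C enrichment | CBF, CBV, CMRO2 |
|---|---|---|
| Region | MRS voxel | Same voxel, overlaid on the maps |
| Tissue correction | Gray and white matter components applied to the curves | None stated |
| Tissue covariate in the comparison | None stated | None stated |

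**Attenuation**

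Assumed inputs, none from the documents: gray:white CBF ratio R = 2 to 3; mean gray fraction f = 0.5; between-subject SD of f = 0.05 to 0.10; CV of CBF from other sources = 0.20; f unrelated to tissue-level perfusion and to corrected enrichment.

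- Voxel CBF is proportional to 1 + (R − 1) × f.
- CV due to tissue mix = (R − 1) × SD of f / [1 + (R − 1) × 0.5].
- Attenuation factor = 0.20 / √(0.20² + CV²).

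| R | SD of f | CV from tissue mix | Attenuation factor | Loss |
|---|---|---|---|---|
| 2 | 0.05 | 0.05/1.5 = 0.033 | 0.986 | 1.4% |
| 3 | 0.05 | 0.10/2.0 = 0.050 | 0.970 | 3.0% |
| 2 | 0.10 | 0.10/1.5 = 0.067 | 0.949 | 5.1% |
| 3 | 0.10 | 0.20/2.0 = 0.100 | 0.894 | 10.6% |

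A true correlation of 0.50 would therefore appear as 0.50 × 0.894 = 0.45 to 0.50 × 0.986 = 0.49.

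**Simulation on wider assumptions**

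Twenty thousand replicates were run with mean gray fraction 0.55, SD 0.05 to 0.15, gray:white ratio 2 to 3 for perfusion and for enrichment, and tissue-level CV 20%. With enrichment corrected and perfusion not, a true 0.50 falls to 0.40–0.50. Power of a two-sided 5% Pearson test falls from about 33% to 21–32% at n = 10, and from about 50% to 33–48% at n = 15. The lower ends come from an SD of 15 points. With a true correlation of zero, the estimate stays near zero and type I error stays at about 5%.

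**Compared with sampling error**

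For an observed r of 0.50, Fisher's z is 0.549, with standard error 1/√(n − 3).

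- n = 10: 0.549 ± 1.96 × 0.378 gives a 95% interval for r of −0.19 to 0.86.
- n = 15: 0.549 ± 1.96 × 0.289 gives −0.02 to 0.81.

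A loss of 0.01 to 0.05 in r is far inside either interval.

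**A group shift, if there were one**

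At R = 2.5, a 10-point difference in gray fraction would move voxel CBF by 1.5 × 0.10 / (1 + 1.5 × 0.5) = 0.15/1.75 = 8.6%. The 10 points are a what-if value.

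**The case against.** The strongest reply is that the plan is silent on a perfusion correction and does not exclude one. That stands. The perfusion section rules out no tissue step, and the anatomical images are acquired for segmentation in general, not for spectroscopy alone. A reader might infer that perfusion will be a plain uncorrected voxel average, but the text names no summary measure at all. The point is that the step is not specified.

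Second, the form of the 13C correction is not given. The text says only "tissue components will be calculated and applied as correction to factors to the" curves. A reader might infer that gray:white variation is fully removed from enrichment, but that does not follow. If the correction scales for total brain tissue, the gray:white mix stays in both variables. The risk would then run the other way: with neither side corrected, the simulation gave a spurious correlation of about 0.02 to 0.33 when the true value was zero. It is also an inference, though the natural one, that the final enrichment pools are the corrected values. This objection limits how firmly attenuation can be claimed. It does not remove the need for one stated treatment of both sides.

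Third, the remedy has limits. A single voxel mean cannot be split into gray and white perfusion without an assumed perfusion ratio, and the documents describe no CSF fraction to borrow. Averaging by tissue class means registering 1 mm anatomical images to 5 mm perfusion slices with a 20% gap, where many pixels are mixed. These points stand and shape the fix.

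Fourth, every input to the size calculation is assumed, and the Statistical Analysis section puts its emphasis on descriptive and graphical statistics. That supports a low priority.

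**Conclusion.** The point holds as a modest, inexpensive improvement. Tissue composition is specified as a correction for enrichment and not for the perfusion values set against it, and nothing elsewhere closes the gap. On the natural reading, the correlation for the second objective is attenuated by about 1% to 11%. That rests on the assumed gray:white ratio of 2 to 3, gray fraction 0.5 with SD 5 to 10 points, and CBF CV 20%. The figures are for CBF; CBV and CMRO2 would need their own ratios. Imprecision from 10 patients and 5 controls is much larger.

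Two stronger readings are not supported. A reader might infer that one-sided correction produces a false correlation. It does not when gray fraction is unrelated to corrected enrichment. A reader might also infer that patients and controls differ in gray fraction because the voxel is placed away from contusion. That is a possible route, since the constraint bears on patients and not on healthy volunteers, but the documents give neither a direction nor a size and do not show that a difference occurs.

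**What to change.** In the DSC-Perfusion Weighted imaging section, state one treatment of tissue composition for both variables, and name the summary measure for perfusion. Either of two routes would serve:

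- **Simpler:** report the perfusion–enrichment correlation adjusted for the voxel gray-matter fraction already computed for spectroscopy (a partial correlation), beside the unadjusted one. This also covers the case where the 13C correction leaves some gray:white variation in enrichment. It costs one degree of freedom: 8 to 7 with 10 subjects, 13 to 12 with 15.
- **Fuller:** coregister the existing segmentation to the perfusion maps, and summarise CBF, CBV and CMRO2 by tissue class within the voxel. This takes some image processing, and mixed pixels in 5 mm slices will limit how cleanly the classes separate.

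In the voxel tissue composition section, add a sentence giving the form of the 13C correction and confirming that the final enrichment pools are the corrected values. Tabulating the gray-matter fraction by group would show directly whether patients and controls differ. Neither route needs extra scanning.

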### Tracking the Metabolic Fate of Glucose: $^{13}\text{C}$ -MR spectroscopy

In order to determine how glucose is being metabolized,  $^{13}\text{C}$  MRS offers an attractive, novel method to study alterations in multiple enzyme complexes following a TBI. The primary advantage of this technique arises from its ability to distinguish  $^{13}\text{C}$  incorporation into multiple metabolites as well as into the specific carbon positions within the same metabolite, resulting in a detailed analysis of the metabolic fate of  $^{13}\text{C}$  label . The relative  $^{13}\text{C}$  enrichment at each carbon position and the ratios between isotopomers of Glu and Gln gives additional information regarding enzyme usage and metabolic compartmentation . The acquisition of  $^{13}\text{C}$  spectra over time enables the dynamic measurement and calculation of in vivo rates of flux through metabolic pathways, an important technique to study in vivo cerebral metabolism. To our knowledge, the use of  $^{13}\text{C}$  glucose together with  $^{13}\text{C}$  acetate to measure metabolic flux simultaneously has not been performed in either the normal or injured human brain. In this study, we will use of [1- $^{13}\text{C}$ ] glucose together with [1, 2  $^{13}\text{C}_2$ ] acetate to measure changes in both neuronal and astrocyte metabolism in both TBI and control subjects.

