### **Study Objectives**

The goals of this inter-departmental study are: 1) the clinical application of in vivo  $^{13}\text{C}$  MRS at 3T to identify specific metabolic alterations following TBI and 2) determine if changes in cerebral perfusion effect metabolism by limiting metabolic substrate flow into the brain following TBI.

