### **In vivo C MRS**

#### [1-C] glucose and [1, 2-C2] acetate infusion protocol

To reduce the complicating effects of endogenous glucose or the conversion of acetate to glucose in the liver, both control and TBI subjects will undergo a hyperinsulemic euglycemic glucose clamp via insulin infusion (60mU · m^-2 · min) in conjunction with a variable infusion of 20% dextrose solution. Following the insulin clamp, 30 ml of 100% isotopically enriched [1-C] glucose and [1, 2-C2] acetate (Cambridge Isotope Laboratories, Andover, MA, USA) in a 20% w/v solution will be infused for 10 minutes followed by a constant infusion (3mg · kg · min) of 30% isotopically enriched [1-C] glucose and [1, 2-C2] acetate. This infusion protocol results in normoglycemic plasma glucose levels of ~ 5.3 mmol/L, which will be maintained for the duration of the C MRS experiment. Blood samples (0.5ml) will be drawn in duplicate at 5-minute intervals for the immediate measurement of plasma glucose level using an Accu-Chek glucose meter and for measuring plasma glucose and acetate isotopic enrichment by high-resolution H and C NMR spectroscopy.

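### Objective 2 is tested only against final Glu and Gln enrichment, which may carry little information about metabolic rate; the planned flux parameters should be compared with perfusion alongside it

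*Combined protocol and SAP*

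**What the plan says.** Study Objectives gives the second goal as to "determine if changes in cerebral perfusion effect metabolism by limiting metabolic substrate flow into the brain following TBI". The DSC-Perfusion Weighted imaging section puts this into practice: CBF, CBV and CMRO2 inside the MRS voxel are compared with the final "Glu and Gln enrichment pools to determine if substrate limitation correlates with metabolite enrichment". That section does not mention flux, and does not say whether its final enrichment is a corrected value.

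Flux is planned elsewhere. The section on tracking the metabolic fate of glucose says that acquiring "spectra over time enables the dynamic measurement and calculation of in vivo rates of flux through metabolic pathways". The ISIS-DEPT section plans flux parameters from a two-compartment model "implemented in CWave software using modifications of previously published equations". Statistical Analysis names Pearson correlations of metabolic or perfusion changes with neurological status, but not of perfusion with metabolism.

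On plasma input, the infusion protocol draws blood every 5 minutes, among other things "for measuring plasma glucose and acetate isotopic enrichment by high-resolution" NMR. It describes an insulin clamp "in conjunction with a variable infusion of 20% dextrose solution", then a 10-minute infusion of fully enriched substrate, then a constant infusion at 30% enrichment. Normal plasma glucose is a level "which will be maintained for the duration of the" MRS experiment.

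Two corrections are planned. Plasma NMR spectroscopy corrects brain isotopomers for peripheral metabolism, and its stated reason is labelled glucose that the liver makes from acetate. The voxel composition section says that "the relative gray matter and white matter tissue components will be calculated and applied as correction to factors to the" enrichment curves.

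**The concern.** The objective concerns supply and the rate at which substrate is used. Final enrichment is an end-point, and two features make it an uncertain stand-in for rate.

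- **Plateau.** Once the Glu and Gln pools have nearly equilibrated with their precursor, a faster or slower brain reaches much the same level.
- **Precursor input.** The glucose-derived label scales with plasma glucose enrichment, which depends on whole-body glucose handling. Neither planned correction is described as normalising to each subject's precursor curve.

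If perfusion did limit metabolism, the planned correlation could still be near zero, and a reader could not tell that from a true absence of substrate limitation. The time-course spectra, plasma samples and flux model that could help to separate the two are already in the protocol.

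**Working it through.** The plan gives no figure to reproduce, so the check is illustrative.

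**Inputs from the protocol.** Plasma glucose about 5.3 mmol/L; 30 ml of a 20% w/v solution (6 g) over 10 minutes at 100% enrichment; then 3 mg/kg/min at 30%; 60 minutes of 13C acquisition (Table 1).

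**Assumed, not in the documents.** Weight 70 kg; glucose distribution volume 0.2 L/kg; infusate all glucose; clamp continuing with unlabelled dextrose; whole-body disposal D of 4, 6 or 8 mg/kg/min; final reading 70 minutes after the label starts (10 + 60); Glu turnover k of 0.01 to 0.10 per minute.

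**Model.** Glucose pool = 5.3 × 0.18 × 0.2 = 0.1908 g/kg, or 190.8 mg/kg. Brain label follows dE/dt = k × (Ep/2 − E), where Ep is plasma enrichment.

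**Sensitivity to brain rate (D = 6, k halved).** As a cross-check, a constant-input model E(T) = Ep × (1 − exp(−kT)) with T = 60 gives a change on halving k of 1/(1 + exp(−30k)) − 1.

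| k per min | Final E at k | Final E at k/2 | Change | Change, constant input |
|---|---|---|---|---|
| 0.01 | 6.03% | 3.57% | −41% | −43% |
| 0.03 | 10.0% | 7.69% | −23% | −29% |
| 0.06 | 10.5% | 10.0% | −4 to −5% | −14% |
| 0.10 | 10.1% | 10.5% | +5% | −5% |

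The small rise at 0.10 arises because plasma enrichment falls after the fully enriched infusion, and a faster pool follows it down. Both models show the response shrinking as k rises.

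**Sensitivity to plasma input (identical brain, D = 4 against 8).** Final E is 13.05% against 7.83% at k = 0.03, a ratio of 1.67. At k = 0.06 it is 14.48/7.86 = 1.84, and at 0.10 it is 14.42/7.34 = 1.96. Under other modelling choices the ratio is 1.44 to 1.66 over the same k, and 1.34 at the lowest when k = 0.01 is included. If half the label is glucose-derived, it is 1.29 to 1.41. If the clamp stops and endogenous output is 0 against 2 mg/kg/min, it is 1.31 to 1.39.

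**Simple normalisation.** With this non-steady plasma curve, dividing by mean plasma enrichment leaves a 4-against-8 ratio of 1.16 to 1.36, and dividing by final plasma enrichment gives 0.80 to 0.95. With constant plasma enrichment, division removes the dependence entirely. The answer depends on the plasma curve, which is not known in advance.

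**Which mechanism matters more.** Trials of 10 patients were simulated with a true correlation of 0.70 between perfusion and log k, and spectral noise of 0.5 to 2 percentage points. With no variation in disposal at all, final enrichment gave a mean r of 0.22 to 0.53 at k = 0.03, −0.06 to 0.01 at 0.06 and −0.27 to −0.09 at 0.10. Adding disposal variation (CV 25%) lowered r mainly at k = 0.03, to 0.16 to 0.24. Loss of rate information is therefore the main driver at moderate to fast turnover, and precursor variation is a further one.

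**The case against.** Several points on the other side stand.

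- **The plan does not ignore plasma enrichment.** It measures it every 5 minutes and plans a correction based on all plasma glucose isotopomers. A reader might infer that final enrichment is left uncorrected; the text does not say so. What stands is that the stated purpose is liver-made glucose, and normalisation to each subject's input is not stated.
- **The loss may be modest.** At k = 0.01 to 0.02 the simulated correlation with final enrichment is 0.26 to 0.51 if the clamp continues and 0.38 to 0.63 if it stops. At k = 0.03 with the clamp stopped it is 0.28 to 0.49. The infusion protocol can be read either way on the clamp.
- **Flux is not shown to be superior in practice.** In the simulations fitted turnover gave r of 0.53 to 0.67, but the fit had one parameter and used the model that generated the data. The real fit has two compartments and two tracers, with about 3,600 s / (128 × 2.5 s) = 11 spectra per subject. The protocol itself describes the two-tracer measurement as new in humans.
- **The study is exploratory.** The analysis is mainly descriptive and graphical, in 10 patients and 5 controls. Enrichment is the more direct, less model-dependent measure. Background plans to relate perfusion to glucose and acetate metabolism generally, so a flux comparison is not excluded.

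These points limit the claim to adding a comparison. They do not remove the gap: the only stated test of Objective 2 uses an end-point that may be insensitive to rate.

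**Conclusion.** The point holds in a limited form. As written, Objective 2 rests on final enrichment alone, and a null correlation would be ambiguous. How ambiguous depends on turnover: halving it lowers final enrichment by about 41% at 0.01 per minute but hardly at all at 0.06 to 0.10 in the plasma-curve model (14% and 5% with constant input). These figures rest on assumed turnover, disposal and distribution volume, and on one reading of the clamp.

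Two stronger readings are not supported. One is that final enrichment mainly reflects plasma dilution: the simulated loss at k of 0.06 and above persists without any disposal variation, and the acetate-derived label is not diluted by dextrose. The other is that flux should replace enrichment, with enrichment demoted to secondary: nothing in the documents shows that the two-tracer fit will be stable enough in so few subjects. Nor can the protocol state in advance how much of the dilution a simple division would remove.

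**What to change.** In the DSC-Perfusion Weighted imaging section, add a comparison of voxel CBF, CBV and CMRO2 with the flux parameters from the ISIS-DEPT section, fitted with each subject's own 5-minute plasma glucose and acetate enrichment curves as input. Name it in Statistical Analysis, and say that Objective 2 will be answered from this comparison and the final-enrichment comparison together, both exploratory.

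Report each subject's final Glu and Gln enrichment beside that subject's plasma enrichment curve, and say whether the value is corrected. List every subject whose flux fit fails. State that a null enrichment correlation alone will not be read as evidence against substrate limitation.

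The cost is analysis text only: no new scan, blood sample or patient is needed. The downside is reliance on a two-tracer, two-compartment fit in few subjects. Even in the favourable one-parameter simulation, raising spectral noise from 0.5 to 2 percentage points lowered the fitted correlation from 0.65–0.67 to 0.54–0.60. That is why enrichment should stay in the analysis.
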